7.4 Medication Pre-Induction

7.4.1 Vivitrol Pre-Induction

Vivitrol Pre-administration and Injection Procedures. Individuals must be free from opioids for at least 7 days before receiving the Vivitrol injection, which is confirmed via self-report and facility records. To ensure opioid abstinence at time of induction, a naloxone challenge will occur followed by one day of oral naltrexone before Vivitrol injection, adhering to NIDA-approved and IRB-approved procedures. Subsequent Vivitrol injections administered every four weeks will require confirmation of opioid abstinence by either naloxone challenge or administration of oral naltrexone, as determined appropriate and necessary by the Study Physician and/or Nurse Practitioner (NOTE: In New Mexico, a Nurse Practitioner [NP] has virtually all the same medical privileges as a Physician and can function as an Physician).

The pre-induction strategy includes:

- *Step 1.* Participants must self-report no clinically significant opioid use (i.e., at any level that could constitute a potential risk of precipitating opioid withdrawal upon naloxone administration in the next step) in the previous seven days.
- *Step 2.* A urine drug screen will be administered shortly before the naloxone challenge and must be negative for opioids. Individuals who are opioid-negative will continue in the pre-induction process. Individuals may have an additional urine drug screen on a subsequent day if the study medical clinician determines that a second screen is appropriate.
- *Step 3.* Completion of all pertinent psychosocial and medical screening and eligibility assessments.
- Step 4. Absence of opioids in a urine screen is not absolute proof that a patient is entirely opioid-free; As such a naloxone challenge will be administered. Prior to subsequent Vivitrol injections every four weeks, the naloxone challenge can be performed at the discretion of the study physician to ensure continued suitability for the Vivitrol injection. An example of a naloxone challenge procedure may begin with I.V., I.M., or subcutaneous delivery of 0.1mg naloxone. If no significant opioid withdrawal symptoms appear after a few minutes, a second dose of 0.3mg would then be administered followed by a brief observation period. With no observed discomfort, 0.8mg naloxone would then be administered as the final dose, followed by an observation period. A minimum 0.8mg bolus must be given before determining the outcome of the challenge. An alternative is to challenge with a single 0.8mg bolus. The determination as to whether the participant is eligible to continue on to VI induction will be made by the study medical clinician based on clinical judgment, including both objective and subjective assessments. Attention to individual symptoms and symptom changes should guide determination of eligibility. Signs of discomfort or an increase in withdrawal symptoms following naloxone administration should be taken as a positive result of the challenge, with induction delayed until a negative challenge result is achieved.

Participants who experience withdrawal symptoms following the naloxone challenge can be treated with ancillary medications if appropriate, observed until symptoms resolve, and given the opportunity to be re-challenged on a future date. Participants who are not interested in continuing to participate, or who fail a repeat naloxone challenge, will not be eligible to participate.

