2.4 Interventions

All participants will be scheduled for twice-monthly medical management and assessment appointments for the first three months of the 24-week post-release intervention phase, with monthly appointments for months 4-6. Eligible participants will be randomly assigned to treatment condition (VI, PNV, DE) in equal numbers. VI and PNV participants will undergo a naloxone challenge to ensure opioid abstinence at the time of Vivitrol induction. Those in the PNV condition will be provided with a PN who will facilitate attendance at outpatient treatment programs as well as assist with other needs. The DE group will not receive any medication but will be scheduled for assessments and education on drugs of abuse, maintaining abstinence, and methods for avoiding overdoses on the same schedule as the other two groups. The DE group will also be

provided with naloxone kits to be used in the event of overdose. All groups will also be provided with referrals to community-based substance abuse treatment programs.

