5.2 Duration of Study and Clinic Visit Schedule

The duration of this study will include a projected 2-4 weeks for screening/baseline assessments and medication induction, and a 24-week intervention phase to include, specific to assigned condition, medication, PN, DE, assessments, and medical management. The screening phase will differ in the length of time needed to complete eligibility assessments, random assignment, and to complete medication induction in the VI and PNV conditions. Induction will be scheduled to occur within 4 weeks of discharge. Screening assessments will include the collection of laboratory samples and medical assessments to ensure participant safety. Confirmation of opioid-free status (UDS and naloxone challenge) before medication induction will take approximately two hours. Assessment visits at 1, 3, 6, 7, and 12-months will take about 30-60 minutes depending on the scheduled assessments. Medical management visits will last from 20–60 minutes and will include collection of UDS and other short measures of status and well-being. PN sessions are expected to take about 60 minutes. DE sessions will take about 20 minutes.

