7.2 Screening

The study team will provide a basic description of the study to interested individuals who respond to IRB-approved flyers and announcements at BCMDC. Study staff will verify pre-eligibility status of each study candidate with jail staff (e.g., has completed opioid detoxification, jail term and expected release date). Individuals determined as pre-eligible will be scheduled for a consent/screening appointment. Screening will begin with the informed consent process. A complete medical history and physical exam will occur after consent. Participants will be randomized to study condition when results of all assessments, including blood chemistries and ECG, are obtained and eligibility is confirmed. Screening will take ~4 hours, excluding review of lab results. This process may occur over multiple days.

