7.3 Random Assignment

Eligible participants will be randomly assigned to study condition (VI, PNV, DE) in a 1:1:1 strategy using an urn randomization procedure (Stout et al., 1994) to provide multivariate balance across two characteristics correlated with outcomes in addiction treatment trials: type of opioid (heroin or prescription drug) and gender.

Individuals who terminate participation before induction onto the assigned medication (or similar time-point for behavioral assignments) will be replaced. Those terminating after VI induction or provision of the first DE session will not be replaced and will be counted as "treatment failures" (in an intent-to-treat scenario).

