10.0 STATISTICAL ANALYSES

The project emphasizes evaluation of the clinical utility of Vivitrol in jail inmates as compared with a Drug Education condition (DE), while descriptive statistics will provide an overall assessment of the implementation of the protocol.

Analyses will include an Intent-to-treat (ITT) design such that all randomized participants who received at least one dose of medication (VI, PNV), or received at least one session of drug education (DE) will be included who did not violate the protocol in a way that could potentially affect the efficacy results. Participants will be excluded from the Protocol Population (PP) if:

- 1. concomitant medication that is known to have significant clinical effect on primary or secondary endpoints was administered.
- 2. Violations of the inclusion or exclusion criteria are judged to affect the efficacy evaluations.

Subjects in the PP population will be allocated to treatment groups in the analysis based on the actual treatment they received. If there is substantial difference between the ITT population and the PP population, all analyses described below will be performed using only subjects in this group.

All statistical tests will be performed using two-sided .05 significance levels, unless otherwise stated. All comparisons between treatments will be reported with parameter estimates and 95% confidence intervals. For parameters measured at baseline and subsequently, the variables of interest are changes from baseline.

Post-baseline variables will not be imputed; estimates can be obtained using the hierarchical models specified below under the assumption of missing at random. For the primary outcome measure, diagnosis at six months, subjects who have dropped out for whatever reason will be considered to retain the diagnosis. Other outcome measures for which data are missing will be imputed using multiple imputation methods. Sensitivity analyses will repeat specific analyses using permutation tests of at least 1000 samples.

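### Only VI and PNV must pass an opioid test after randomization; those who never pass are replaced and left out of the 'ITT' set, while comparable DE participants are analysed

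*Combined protocol and SAP*

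**What the plan says.** Randomization comes first. Section 7.2: "Participants will be randomized to study condition when results of all assessments, including blood chemistries and ECG, are obtained and eligibility is confirmed". The naloxone challenge is not named among those assessments.

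The challenge is then assigned by arm. Section 2.4 (Interventions): "VI and PNV participants will undergo a naloxone challenge to ensure opioid abstinence at the time of Vivitrol induction". Section 5.2 lists random assignment ahead of induction in VI and PNV, and gives the time the check takes: "Confirmation of opioid-free status (UDS and naloxone challenge) before medication induction will take approximately two hours". Section 7.4.1 also requires seven days without clinically significant opioid use and an opioid-negative urine screen. The urine screen may be repeated, and a positive challenge is not final at first, "with induction delayed until a negative challenge result is achieved". A second failure is: "Participants who are not interested in continuing to participate, or who fail a repeat naloxone challenge, will not be eligible to participate".

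Two rules then decide what happens to such a person:

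- Section 7.3: "Individuals who terminate participation before induction onto the assigned medication (or similar time-point for behavioral assignments) will be replaced".
- Section 10.0, defining the set it labels ITT: "all randomized participants who received at least one dose of medication (VI, PNV), or received at least one session of drug education (DE".

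No section sets an opioid-negative requirement before a DE session, and none specifies an analysis of everyone randomized.

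**The concern.** Confirming abstinence before giving an antagonist is a necessary safety step. The fault is that its result decides who is followed and analysed, in two arms out of three. DE participants who would have failed the same test are analysed after a single education session.

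If people who cannot pass are also more likely to relapse, removing them from VI and PNV alone makes Vivitrol look better with no drug effect. That link is plausible but is not shown in the documents. Because 7.4.1 ends participation for repeat failers, their month-6 outcomes would not exist, so the bias could be neither measured nor repaired later. Section 10.3 says the results are meant to inform a larger multi-site trial, which would then start from a selected estimate carrying an ITT label.

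**Working it through.** **1. Can the challenge precede randomization?** Section 2.4 gives it to VI and PNV only, and 11.23 ties it to participants in the Vivitrol condition. A test given according to arm must follow assignment.

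**2. Could the oral naltrexone count as the first dose?** No. The order in 7.4.1 is: "a naloxone challenge will occur followed by one day of oral naltrexone before Vivitrol injection". A person who never passes receives no naltrexone, so 10.0 leaves that person out.

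**3. Is early departure itself one-sided?** Declining before the first dose or session can happen in every arm, and 7.3 and 10.0 treat it alike in all three. The asymmetry lies in the opioid test.

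**4. Size of the selection, VI versus DE, no drug effect.** Assumptions, none from the documents: failure fraction f = 5% or 10%; month-6 diagnosis risk p = 55% in those who pass; risk higher by a gap of 20 or 40 points in those who fail. From the plan: 50 per arm (10.3), two-sided 0.05 (10.0).

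Analysed VI risk = p. Analysed DE risk = (1 − f)p + f(p + gap) = p + f × gap. So bias = f × gap. SE = √[p(1 − p)/50 + p_DE(1 − p_DE)/50]. The chance of a false finding for VI is P(Z > 1.96 − bias/SE); the other tail is P(Z < −1.96 − bias/SE).

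| f | gap | bias (points) | DE risk | SE | false finding for VI | two-sided |
|---|---|---|---|---|---|---|
| 5% | 20 | 1.0 | 0.56 | 0.0994 | 3.15% | 5.1% |
| 5% | 40 | 2.0 | 0.57 | 0.0993 | 3.93% | 5.5% |
| 10% | 20 | 2.0 | 0.57 | 0.0993 | 3.93% | 5.5% |
| 10% | 40 | 4.0 | 0.59 | 0.0989 | 5.99% | 6.9% |

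Nominal values are 2.5% and 5%. With p = 45% the chance of a false finding for VI is 3.15-5.95%, almost the same.

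**5. People lost.** To induct 50, an arm must randomize 50/(1 − f): 50/0.95 = 52.6 or 50/0.90 = 55.6. About 3 or 6 randomized people per medication arm leave no outcome.

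**6. Analysing them without following them.** Section 10.0 counts anyone who drops out as still having the diagnosis. Scoring unfollowed failers that way adds f × (1 − p_f) against Vivitrol, where p_f is their true risk:

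- p = 55% (p_f = 0.75-0.95): 0.05 × 0.05 to 0.05 × 0.25 = 0.25-1.25 points; at f = 10%, 0.5-2.5 points.
- p = 45% (p_f = 0.65-0.85): 0.05 × 0.15 to 0.05 × 0.35 = 0.75-1.75 points; at f = 10%, 1.5-3.5 points.

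**7. Power after the fix.** The plan's evaluable sample reproduces: 150 × 0.80 = 120, or 40 per arm. A two-sided t test (78 df, noncentrality d√20) gives 75.5% at d = 0.60 and 59.8% at d = 0.50. Section 10.3 states about 70% and 80% without naming the tests; nothing here depends on that difference. If non-starters gain nothing from assignment, the effect shrinks by 1 − f:

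| d in starters | power, f = 0 | f = 5% | f = 10% |
|---|---|---|---|
| 0.60 | 75.5% | 71.1% (d = 0.57) | 66.5% (d = 0.54) |
| 0.50 | 59.8% | 55.5% (d = 0.475) | 51.1% (d = 0.45) |

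The sample-size multiplier is 1/(1 − f)² = 1.11 or 1.23.

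**The case against.** The strongest reply concerns size. Neither f nor the gap is in the documents. Participants are already detoxified (5.3, 7.2), a positive urine can be repeated and re-challenge is offered, so few may fail. A bias of 1-4 points is small beside a standard error of about 9.9 points, and at f = 5% two-sided error rises by at most half a point. Section 10.3 presents the study as preliminary. This stands, and it limits the severity. Against it, 5.3.1 asks for only 48 hours' detention while 7.4.1 asks for seven opioid-free days, and 7.4.1 itself plans for repeat failure.

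Second, the primary contrast in 10.4.2 pools naltrexone data from NYU and UCLA with methadone data from FRI and omits the PN arm. None of the figures above applies to it. This also stands.

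Third, replacement of challenge failers is inferred: 7.4.1 does not mention it, and 7.3 speaks of people who end participation before induction. The inference is close, because 7.4.1 ends their participation at that point. Even without replacement, 10.0 would exclude them.

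Fourth, 7.13 lets people who opt out of medication continue assessments, and Table 1 schedules urine screens at screening and pre-release in all arms. These would support a sensitivity analysis. But the opt-out provision does not cover people declared ineligible, the never-dosed stay outside the analysis set, and DE urine results carry no pass requirement.

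Finally, follow-up of failers may be incomplete, and step 6 shows that scoring the missing ones as diagnosed can outweigh the original bias: 3.5 points against 2.0 at p = 45%, f = 10%, gap 20. This is a reason to follow them actively.

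**Conclusion.** The concern holds. As written, the plan makes a post-randomization exclusion in two arms only and calls the result ITT. That follows from the text and needs no assumption. The direction, favouring Vivitrol, assumes that people who fail the test have worse outcomes. The size rests on assumed values: 1-2 points at a 5% failure fraction and 2-4 points at 10%, with two-sided type I error of 5.1-5.5% and 5.5-6.9%. The effect is probably modest, so this should be fixed but does not by itself undermine the trial. Confidence is medium because the failure fraction is unknown. The figures describe this study's own VI-versus-DE comparison only.

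**What to change.** 1. In 7.4.1, state that a randomized person who fails the repeat challenge does not receive Vivitrol, in place of losing eligibility for the study. Keep that person in the assigned arm, without replacement, and offer every assessment including the month-6 diagnosis, as 7.13 already does for those who opt out of medication.
2. In 7.3 and 10.0, define ITT as everyone randomized, analysed as assigned whether dosed or not. Keep the dosed or started set as a secondary analysis.
3. Report by arm how many fail or decline before the first dose or session.
4. Keep the urine screen and naloxone challenge before injection as a safety step.

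Optional, to limit dilution: confirm seven opioid-free days and a negative urine in all arms before randomization. This narrows the population by an unknown number of short-stay or urine-positive detainees and is not needed to remove the bias.

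The cost is wording in three sections and no new procedure. The number randomized is 150; under replacement, inducting 50 per medication arm would take about 155 or 161 in all (2 × 52.6 + 50; 2 × 55.6 + 50). The downside is dilution: about 47 or 45 of 50 start in each medication arm, and the estimate is about 95% or 90% of the effect in starters. The power loss shown above is for a t test on a standardized mean difference, so it is only a guide for the binary diagnosis. With full follow-up, dilution is all that remains; incomplete follow-up leaves some bias against Vivitrol through the dropout rule in 10.0.

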7.5 Pharmacotherapy

7.5.1 Extended-release Naltrexone (VI)

Depot Naltrexone as Vivitrol. Vivitrol is a combination of naltrexone-containing microspheres that are delivered by injection every four weeks into the muscles of the buttock. Plasma concentrations of naltrexone and 6-beta naltrexol (its main metabolite) after a single Vivitrol injection are detectable for at least 30 days and must be re-administered to maintain its effect. Continued use of naltrexone is not associated with tolerance or addiction. The most common AE has been reaction at the injection site, reported in 50% of the placebo group and 69% of the 380mg Vivitrol group *Physician's Desk Reference* (PDR). The most common gastrointestinal AEs are nausea (11% in placebo group; 33% in Vivitrol group) and vomiting (6% in placebo group; 14% in Vivitrol group). For pain management in an emergency situation, regional anesthesia or non-opioid analgesics are advised.

Extended-release Naltrexone (VI) will be provided to participants as a gluteal intramuscular injection (380 mg) administered every four weeks. The VI injection shall be administered following the guidelines provided in the package insert, including the pre-induction procedures described above.

Well-developed precautionary procedures will be followed to avoid adverse events associated with induction. For example, body habitus will be assessed during the physical exam at screening to assure that needle length is adequate for intramuscular administration as an inadvertent subcutaneous injection of VI may increase the likelihood of injection site reactions. The needle provided in the VI package is a customized needle required for injection of medication. Individuals whose body habitus precludes a gluteal intramuscular injection of naltrexone using the required needle will be excluded from the study.

7.6 Behavioral Treatment

7.6.1 Drug Education (DE)

This condition is intended as an enhanced treatment-as-usual condition. Enhancements will include standardized materials for drug education and overdose prevention education.

7.6.2 Patient Navigators (PN)

In addition to receiving Vivitrol, participants in the PNV condition will be assigned a Patient Navigator (PN). A PN provides one-on-one assistance to surmount barriers to entry and adherence with medical care for chronic disease. Originally designed to improve outcomes in oncology for disadvantaged female patients, the PN conceptual foundation is a strengths-based case management perspective to help patients keep their appointments (through scheduling, reminders, and accompanying the patients), improve communication between the patient and their providers, offer health education, provide assistance with personal barriers to treatment (e.g., transportation, health insurance, childcare), and offer emotional support. Clinical trials have found that PN increased cancer screening and follow-up rates, improved entry and adherence to HIV treatment, and increased adherence to medical appointments and greater likelihood of achieving an undetectable viral load compared to controls.

Addictions treatment studies have also found positive outcomes in randomized trials for services comparable to PN to increase the likelihood of treatment entry from: a central drug treatment intake; receiving medical care at a hospital; and community outreach. Although a case

management approach was not found effective in linking drug users newly-released from prison to community treatment, that study's sample was heterogeneous in terms of its drug use (only 10% were opioid-dependent) and did not receive pharmacotherapy. PN has not been studied in re-entry into the community with treatment initiated in jail. It is our hypothesis that PN has the potential to assist newly-released detainees to overcome barriers to successful community treatment entry.

In this study, the Patient Navigator (PN) will meet with PN participants to discuss barriers to treatment, facilitate referrals to community outpatient behavioral drug abuse treatment, and provide assistance with other social support-related needs.

7.7 Study Team Training

Research staff will be certified in good clinical practices and will continue to receive regular boosters in clinical research procedures, including protection of privacy and well-being of human research participants.

The PI and Study Physician/Nurse Practitioner and other clinical personnel will receive training in the medication procedures (i.e., preparation for the Vivitrol injection and its administration). The Study Physician will provide on-site training at BCMDC and BCMDC clinical staff may also travel to UCLA to observe medication procedures.

7.8 Medical Management

At each clinic visit, participants will meet with study physicians and other study personnel such as nurses, research assistants, and counselors, to review urine results, discuss adverse events, consider the study medication effects and side effects, and discuss other pertinent issues in keeping with sound medical practice. Participants' engagement in self-help groups such as 12-step is permitted. Medical Management visits will occur twice-monthly during months 1-3, and monthly during months 4-6, and Vivitrol injections will be provided monthly to participants in the VI and PNV conditions.

7.9 "Rescue" Protocol

Participants who develop significant problems, who cannot tolerate naltrexone, or whose preexisting condition worsens during the study may receive increased levels of care deemed necessary by the Study Physician, and they will be referred to other treatment resources.

